4.4 Randomization, blinding and lifting the blind

The randomization process will be centralized. Allocation of a randomization arm to a patient included will be made by IWRS (Interactive Web Response System), on the basis of a unique randomization list for all investigation centers.

The lists of randomization will be pre-established, by the “Pole IMER” at the Hospices Civils de Lyon – Clinical Research Unit.

Clinsight (Ennov clinical) software will be used to manage this study.

During the inclusion visit, after verifying the inclusion criteria, the investigator connects to the platform to include the patients in the eCRF. This will assign an identification number. When inclusion is validated, the patient is randomized and a treatment code is allocated by the system. The treatment is then dispensed by the pharmacy at the Hospital Center.

This will be a double blind study in which neither the patient nor the investigator will be aware of the nature of the treatment administered so as to annul any bias in the follow-up and measurements.

Tubes of Tacrolimus 0.1% or placebo will be identical and will have appropriate labeling.

Should a serious adverse event occur, the main investigator, the co-investigators or the sponsor may request that the Anti-Poison Center in Lyon lift the blind 24h/24h (the phone number is written on the clinical trial participation card). The written detailed procedures for lifting the blind will be given to the investigators and the Anti-Poison Center in Lyon.

All requests for unblinding must be justified. Most often, study drug discontinuation and knowledge of the possible treatment assignments are enough to treat a study patient who presents with an emergency condition. When the investigator asks for unblinding, he/she must provide patient identifying information, the date, and the reason for unblinding. The investigator will be informed of the details of the drug treatment.

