- The physical component and mental component of the SF36 and its domains will be presented in each group at inclusion, at the end of the treatment and at the end of the study. The relative evolution in SF36 (overall and per item) will be computed by subtracting the baseline value from the V2 value (end of the treatment) and the V3 value (end of the study). The delta (V3/V1 & V2/V1) in components and in each SF36 domain will be compared between groups using student t-tests (or Mann-Withney tests in case of non normality). Mixed models will be produced to compare evolution between the groups.
- The ESS will be presented for each group at inclusion, at the end of the treatment, and at the end of the study. The relative evolution in ESS will be computed by subtracting the baseline value from the V2 value (end of treatment) and the V3 value (end of study). The delta (V3/V1 & V2/V1) in ESS will be compared between groups using student t-tests (or Mann-Withney tests in case of non normality). Mixed models will be produced to compare evolution between the groups.
- The biological values (hemoglobin and serum ferritin) will be presented in each group at inclusion, the end of the treatment and the end of the study. The relative evolution in hemoglobin and ferritine levels will be computed by subtracting the baseline value from the V2 value (end of treatment) and the V3 value (end of study). The delta (V3/V1 & V2/V1) in biological measures will be compared between groups using student t-tests (or Mann-Withney tests in case of non normality). Mixed models will be produced to compare the evolution.

Systemic tacrolimus Tacrolimus systemic absorption: the percentage of patients who present with systemic absorption of KK506 will be calculated. If tacrolimus is detected in the blood the level of exposure will be listed.

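### Secondary efficacy measures are tested on raw change from V1, and the added mixed models do not say how V1 enters; naming one baseline-adjusted model would probably narrow the intervals at almost no cost

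*Combined protocol and SAP*

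**What the plan says.** Section 9.2.2.5 defines the quantity to be tested as a subtraction, although it calls it relative and labels it as a quotient. For ESS: "The relative evolution in ESS will be computed by subtracting the baseline value from the V2 value (end of treatment) and the V3 value". The test follows: "The delta (V3/V1 & V2/V1) in ESS will be compared between groups using student t-tests", with Mann-Whitney as the fallback for non-normal data. The other measures match. For SF-36: "The delta (V3/V1 & V2/V1) in components and in each SF36 domain will be compared between groups using student t-tests". For hemoglobin and ferritin: "The delta (V3/V1 & V2/V1) in biological measures will be compared between groups using student t-tests". The preceding bullets of the section use the same scheme for nosebleed duration, nosebleed number and red cell transfusions.

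Each bullet closes with a second analysis, for example "Mixed models will be produced to compare evolution between the groups". Nothing is said about covariates, the role of V1, the covariance structure, or which of the two analyses is the reported result. No baseline covariate is named anywhere in section 9.2.

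Section 4.4 describes allocation "on the basis of a unique randomization list for all investigation centers" and states no stratification factor. Section 9.1 plans 24 patients per arm. Section 6 and Table 1 show that all of these measures are collected at V1, V2 and V3.

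**The concern.** A change score adjusts for baseline with a slope fixed at 1. If the true regression of follow-up on baseline is flatter, which is usual for measures that fluctuate, the change score over-corrects: patients who start high tend to fall more in either arm. The result is a wider interval than necessary and an estimate that partly reflects any chance difference between arms at V1. With 24 per arm and no stated stratification, some chance difference is to be expected.

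The mixed models could repair this or leave it as it is, depending on how V1 enters. Because they are also not ranked against the t-test, two analyses of one criterion could disagree with no rule for which one counts. At stake is precision on the severity, quality-of-life and biological objectives of a small phase II trial.

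**Working it through.** **The plan's own figure.** Section 9.1 gives 22 per group for 60% versus 15%, Fisher exact test, two-sided 5%, 80% power. Exact enumeration gives power of 79.9% at 21 per arm, 82.7% at 22 and 87.6% at 24. The figure reproduces. It concerns the primary responder criterion only; the plan gives no precision or power figure for the secondary measures.

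**Inputs.** n = 24 per arm (section 9.1). The correlation r between V1 and follow-up, and the SDs, are not in the documents. I assume r from 0.3 to 0.9 and, first, equal SDs at V1 and follow-up, in units where SD = 1.

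**Variance of the estimated arm difference.**

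- Change score: 2(1−r) × 2/n
- Adjusted for V1: (1−r²) × 2/n
- Ratio: (1−r²) / [2(1−r)] = (1+r)/2

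At r=0.5 these are 1 × 2/24 = 0.0833 and 0.75 × 2/24 = 0.0625, a ratio of 0.75.

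**Interval width, with the small-sample cost included.** The adjusted model has 45 rather than 46 residual degrees of freedom, and its variance is inflated by about 1 + 1/(N−4) = 1 + 1/44. The width ratio is √[(1+r)/2 × (1+1/44)] × t(45)/t(46).

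| r | Variance ratio | 95% CI half-width, change | Half-width, adjusted | Width ratio | Simulated trials with narrower adjusted CI |
|---|---|---|---|---|---|
| 0.3 | 0.65 | 0.688 | 0.561 | 0.82 | 99.5% |
| 0.5 | 0.75 | 0.581 | 0.509 | 0.88 | 98% |
| 0.7 | 0.85 | 0.450 | 0.420 | 0.93 | 90% |
| 0.8 | 0.90 | 0.368 | 0.353 | 0.96 | 79% |
| 0.9 | 0.95 | 0.260 | 0.256 | 0.99 | 57% |

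The last column is from 5,000 simulated trials per row with 24 per arm. At r=0.95 the adjusted interval is the narrower one in only 42% of trials. With 22 per arm the width ratios are almost the same (0.82, 0.88, 0.93, 0.96, 0.99).

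**Unequal SDs.** Let k be the V1 SD divided by the follow-up SD. The large-sample width ratio is √[(1−r²)/(1+k²−2rk)]. At k=0.8 it is 0.945 for r=0.5, 0.99 for r=0.7 and exactly 1.0 for r=0.8, where the regression slope r/k equals 1 and the change score is already optimal. At k=1.25 it is 0.756, 0.792 and 0.80 for the same three correlations, a larger gain than with equal SDs.

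**Chance imbalance at V1.** The SD of the difference in V1 means is √(2/24) = 0.29. If that difference is D, the follow-up difference is expected to shift by rD and the change-score difference by rD − D = −(1−r)D. One SD of imbalance therefore moves the change-score estimate by 0.5 × 0.29 = 0.14 SD at r=0.5 and 0.3 × 0.29 = 0.09 SD at r=0.7.

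**The planned mixed models.** I computed the variance of the arm contrast for a model of V1, V2 and V3 with arm-by-visit terms, complete data, 24 per arm and a common correlation of 0.5. With the V1 arm difference left free it is 0.0833, the change-score value. With V1 means constrained equal it is 0.0625, the baseline-adjusted value. The same two identities hold at r = 0.3, 0.7, 0.8 and 0.9.

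**The case against.** The strongest defense is that the section already plans mixed models, and one common form of them has the full precision of baseline adjustment. Section 9.2 also says that it gives the main elements of the analysis plan and that revision is possible before the database is frozen, so some missing detail is to be expected. This stands in part: a loss of precision is possible, not established. It does not close the point, because the other common form gives no gain and the text neither chooses between them nor ranks them against the t-test.

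A reader might also infer four things that the documents do not support:

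- That the change score wastes the baseline value or biases the comparison. It uses V1 with a slope of 1 and is unbiased under randomization.
- That adjusted intervals are certain to be narrower. This depends on r and the SD ratio, which the documents do not give. For ESS, two of the six items in Appendix 2 ask whether something has ever happened; as worded they cannot revert from yes to no, which plausibly raises r and shrinks the gain.
- That a V1 imbalance of 0.29 SD passes whole into the estimate. Only the fraction (1−r) does.
- That the change has no downside. It costs one degree of freedom, and the plan's Mann-Whitney fallback needs a place beside a parametric main model.

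**Conclusion.** The point holds as an improvement in efficiency and a needed clarification, not as the correction of an invalid test. The stated tests on change are valid but use a fixed baseline slope, and the mixed models are too loosely described to tell whether they recover the lost precision. With 24 per arm and equal SDs, adjustment narrows the 95% CI by about 18% at r=0.3, 12% at r=0.5, 7% at r=0.7, 4% at r=0.8 and 1% at r=0.9. At r=0.5, ignoring the small-sample cost, 48 adjusted patients are worth 48/0.75 = 64 analyzed by change score. The gain can be nil if the V1 SD is smaller than the follow-up SD. All of this rests on assumed correlations and SD ratios.

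It would be wrong to read this as a doubt about the trial's main result: only secondary criteria are affected, and neither the primary Fisher test nor the 48-patient sample size depends on it.

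**What to change.** Before database freeze, amend section 9.2.2.5 as follows.

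- For ESS, the SF-36 components and domains, hemoglobin and ferritin, name one mixed model as the reported analysis: V2 and V3 values as outcomes, with arm, visit, arm-by-visit and the V1 value as covariate. A model with V1 as an outcome and baseline means constrained equal across arms is an acceptable alternative; state which is used.
- Analyze ferritin on the log scale and report the arm effect as a ratio.
- Report the adjusted difference (ratio for ferritin) with its 95% CI at V2 and at V3.
- Keep the t-test or Mann-Whitney on change as a sensitivity analysis and as the check under non-normality.
- In the same place, state how V1 is handled in the mixed models for nosebleed duration, nosebleed number and transfusions.

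The cost is SAP wording and one degree of freedom. No new data, visits or patients are needed.

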9.2.2.6 Handling of missing values/censoring/discontinuations

Follow-up of patients will be pursued regardless of the situation, except if the patient withdraws his or her consent. In the case of nasal surgery during the study period or any other treatment that is a substitute to the studied treatment, the patient will be followed up but his or her results will be considered as a failure.

The main judgement criterion is based on grids that are filled in daily. Patients are used to these grids and fill them in carefully; the daily durations are summarized over 6 weeks. However if one day is missing, the value will be replaced by an average of the 4 values before and the 4 values after the missing value. This strategy will be applied up to 7 missing values over 6 weeks (i.e. 10%).

If more than 7 days and less than 21 days (included) are missing, a daily average will be computed from the data available (from the 6-week period evaluated) and will be multiplied by 42 to obtain the overall estimated duration.

If a patient is lost to follow-up or refuses to communicate his nosebleed grids or has more than 21 days missing on his grids, the result for the concerned patient will be considered as a failure.

10 Quality assurance

The Clinical research associate mandated by the sponsor is responsible for inspecting the case report forms in conformity with the monitoring schedule for the study, throughout the study, verifying that the protocol is being respected, as well as the totality and the conformity of the source documents, the coherence of the data and that the regulations governing good clinical practices are being respected. The Clinical research associate mandated must have access to the medical files of the patients and other files in relation to the study needed to verify the data entered in the study's electronic case report forms.

The controls of presence, verisimilitude, and coherence will be carried out electronically in accordance with the rules defined in advance. Requests for information will be generated when possible errors are detected.

The health authorities and/or an independent auditor mandated by the sponsor may audit any investigation site, or the sponsor, throughout the duration of the study or after the end of the study so as to control how the study is being conducted and the quality of the data. The investigator must provide direct access to the source documents, and the sponsor to the regulatory documents.

11 Ethical and regulatory aspects

The study will be conducted in conformity with the protocol, the guidelines from the French and European Good Clinical Practices, the Helsinki declaration in its most recent version (Seoul 2008), as well as the recommendations of the ICH (International Conference on Harmonization), and in conformity with the law covering research involving the human person in the French Public Health Code (Law 2012-300 of March 5, 2012).

11.1 Qualification of the research and patient information

In accordance with Law n°2012-300 of March 5, 2012 of the French Public Health Code, this is considered as research involving the human person. The study effectively concerns a drug, called tacrolimus. This drug is not generally used locally in nosebleeds in patients with HHT, but is instead administered topically in the treatment of dermatitis.

11.1.1 Information sheet

Patients may only participate in this study if they have given their written informed consent. To do so, they will first receive spoken and written information from their doctor on: the aim of the study, the duration of their participation, the procedures that will be followed, the benefits, the predictable risks, the disadvantages that may result from the treatments administered or examinations undergone, the confidentiality of the data, insurance cover, and management of the costs associated with this study.

All this information will be summarized in an information sheet that will be given to each patient.

11.1.2 Enlightened consent

Patients may only participate in this study if they have given their written informed consent. Two copies of the consent form will be signed by the subject and the investigating doctor. One copy of this document will be given to the person participating in the study, and the investigator must keep the second copy in his or her archives for a minimum period of 15 years.

11.2 Benefit / risk ratio

All the surgical treatments currently on offer are aggressive for the nasal mucosa and present a risk of perforation of the nasal septum.

Patients' participation in this study will not compromise their possibility for future medical or surgical treatment.

The expected adverse events in this study are:

- Skin burning or irritation at the application site (approximately half of the patients). These symptoms are usually mild to moderate and generally go away within one week of using Protopic. Administration could be easily stopped in case of adverse reaction.
- The risk of systemic adverse events related to tacrolimus is low given the very low doses of tacrolimus administered to the patients. Tacrolimus in blood is monitored and the treatment will be stopped in case of absorption.
- Risk for the blood test may be of the hematoma type at the puncture point or fainting.

If the efficacy of the treatment is shown, the treatment will be proposed to all the patients who have received the placebo.

The risk / benefit ratio for a patient participating in this study is thus perfectly acceptable.

11.3 Confidentiality of the data

Everyone taking part in the study will be bound by the confidentiality agreement regarding the protocol, and linked by professional confidentiality with regard to the participants.

The information sheet will summarize the rights of access of the participants to the nominative information concerning them either directly or indirectly.

All the data collected will be processed anonymously and will be covered by the laws of medical confidentiality.

On the case report forms, or on all other documents, the patients must be identified by their initials and their study number only.

We request that the investigator allow the representatives of the sponsor and/or legal authorities to have direct access to the patients' original medical files for verification of the procedures of the study and the data. The investigator must inform the patient that the files concerning him or her and in relation to the study will be reviewed by the aforementioned representatives without any breach of confidentiality.

11.4 Confidentiality and Good Clinical Practices

In conformity with the dispositions regarding the confidentiality of the data to which the people in charge of controlling the quality of the biomedical research will have access (article L.1121-3 of the French public health code), those people with direct access will take all the precautions necessary with a view to ensuring the confidentiality of the information concerning the people participating in the study and in particular with regards to their identity and the results obtained.

These people, as well as the investigators themselves, are subject to professional confidentiality restrictions (in accordance with the conditions defined by articles 226-13 and 226-14 of the French penal code).

During the biomedical research, or after its termination, the data collected on the people taking part will be rendered anonymous by the investigators (or any other specialized people).

These data must not under any circumstances reveal the names of the participants or their addresses. Only the initials of the subjects will be recorded, accompanied by a code number specific to the study and that indicates the chronological order of inclusion of the subjects.

Every person agreeing to participate in the research will have given his or her written agreement to have access to the individual data concerning him or her and which is strictly necessary for controlling the quality of the research.

11.5 Submitting the protocol to the CPP and ANSM

A request for authorization will be sent by the sponsor of the study to the ANSM. The protocol will be submitted to a randomly selected French CPP for assessment.

11.6 Amendments to the protocol

Any modifications to the protocol will be validated by the Scientific Committee and the sponsor of the study and submitted to the selected CPP and the ANSM for authorization if applicable.

11.7 Computerization of the data

The information collected during this study will be the subject of data processing. The file will be declared at the CNIL and will be put together in conformity with the law governing information technology, files and personal rights (law 78-17 of January 6, 1978, modified by law 2004-801 of August 6, 2004): commitment to conformity with the MR-001 (deliberation n°2016-262 of July 21, 2016).

In conformity with the Information Technology and Freedom law currently in force, patients have the right to access, communicate, oppose and rectify any nominative information. This right can be exercised directly by the patient or by the doctor of his or her choice from the doctor investigators participating in the study.

11.8 Curriculum vitae and signature of the protocol

Before starting the study, the main investigator will provide the representatives of the sponsor with a copy of his or her signed and dated personal curriculum vitae, as well as that of his or her co-investigators, and a signed and dated (signature page) copy of the final protocol of the study.

11.9 Insurance

The Hospices Civils de Lyon ([name]) will be the sponsors of the study and will take out an insurance policy in their name and at their expense (Compagnie SHAM, [name], contrat n°XXXX).

11.10 Study report and publications

The final report of the study will be written in collaboration with the investigator, co-investigators and person responsible for analyzing the data.

This report will be submitted to each of the investigators for approval and once a concensus has been obtained, the final version will be officially approved by the signature of each of the investigators.

The results, regardless of their nature, will be submitted for publication in the international journals with peer review committees interested in this disease.

One main publication is planned, and will focus on the efficacy of nasal administration of tacrolimus on the population studied. The main investigator will write and sign the article as the leading author, providing the main results from the study. The other authors will include the co-investigators, and a representative of the department having carried out the statistical analysis. The ranking of the authors will be decided by concensus, validated ultimately by the main investigator.

Indication of the sponsorship by the Hospices Civils de Lyon will be made in all or any publication.

12 Organization of the study

12.1 Scientific committee

The Scientific Committee for the study, presided over by the study's main investigator, will be composed of investigators (one ENT specialist, one geneticist), the methodologist and the sponsor of the study. The committee will be responsible for validating the definitive version of the protocol, supervising the implementation and running of the study, and for writing the reports and publications resulting from the study.

12.2 Independent monitoring and safety committee for the study

Monitoring the safety of administration of the product, motivated by the iatrogenic risks, justifies the setting up of a specific independent monitoring and safety committee.

This committee will meet as defined in paragraph 2.3. The first meeting will occur after collection of adverse events and observance of the treatment after 30 days for the 8 first patients included.

The committee will give its recommendations on the continuation of the study.

DSMB recommendations will be forwarded to ANSM for information.

There will be two or three meetings depending on the tolerance of the product.

It will be composed of:

- a specialist of the disease not involved in the study,
- a ENT specialist,
- a statistician specializing in the methodology of clinical trials.

13 Medium and long term perspectives

Nosebleeds are a significant morbidity factor in HHT, not solely because of the anemia they provoke, but also because of the handicap that they represent in the daily lives of active patients.

In total, around 95% of the patients followed for HHT are concerned by nosebleeds. Although the mortality rate for the patients followed for this disease is low, the morbidity rate is severe and the psychosocial impact of HHT is almost constant in adults.

For most patients with severe nosebleeds, a regular nasal administration of tacrolimus should make it possible in terms of clinical development to:

- obtain a significant reduction in nosebleed duration.
- decrease the monthly number of nosebleeds,
- increase hemoglobin and serum ferritin concentrations,
- decrease the number of local surgical and packing treatments, as well as the intravenous perfusions of iron,
- decrease the number of blood transfusions sometimes needed in case of a too great loss of blood,
- improve air flow and decrease nasal obstructions,

- improve patient quality of life (possibility of going shopping, going to a restaurant, enjoying meals with family, having a professional activity, etc.),
- decrease the number of consultations and/or hospitalizations,
- decrease the cost of management of severe nosebleeds given their current costs (transfusions, iron supplementation, etc.).

